
months. This survey has excellent reliability and validity, including predictive validity for cardiovascular disease outcomes, and compares favorably to 7 day recall. (Note. We acknowledge that objective measures of physical activity have been found to be more reliable in bariatric samples.141 However, as change in physical activity is an outcome of secondary interest, we have elected to use a well-known self-report measure. We hypothesize that changes in quality of life, dietary intake, and physical activity will be associated with changes in weight. Social Support: The Medical Outcomes Study Social Support Survey is a brief, multidimensional, self-administered, social support survey that was developed for patients in the Medical Outcomes Study (MOS), a two-year survey that was developed for patients with chronic conditions. This survey was designed to explore various dimensions of functional social support, including emotional/informational support, tangible support, affectionate support, and positive social interaction. Sherbourne and Stewart (1991) found that the support measures are reliable (all Alphas 0.91), and are fairly stable over time. Selected construct validity hypotheses have been supported. Prevalence and Control of Chronic Diseases: 1) T2D will be identified using hemoglobin A1c (HbA1c) and glucose measurements obtained from fasting blood samples, and will be defined as HbA1c 6.5% and glucose 7.0 mmol/L (126 mg/dL), or use of antidiabetes medication.36 Prevalence will be calculated using number of participants with T2D as the numerator and total number of participants as the denominator. Controlled T2D, among individuals diagnosed with T2D, will be defined as HbA1c 7.0%.36 These labs are drawn as part of standard clinical care and the HbA1c and glucose results will be extracted from the EMR of enrolled participants. Participants will not be asked to have additional blood draws as part of the study. 2) Hypertension: systolic blood pressure (SBP) and diastolic blood pressure (DBP) will be measured using a Dinamap 9300XL monitor.. Using recently updated US guidelines, hypertension will be defined as SBP130 mm Hg, or DBP80 mm Hg, or use of antihypertensive medication.39 Prevalence will be calculated using number of participants with hypertension as the numerator and total number of participants as the denominator. Controlled hypertension, among individuals with hypertension, will be defined as SBP130 mm Hg and DBP80 mm Hg.39 Blood pressure is measured as part of standard clinical care. SBP and DBP will also be extracted from the medical record of enrolled participants from their preoperative testing with the bariatric surgery program as well as their postoperative follow up with the surgical team. Participants will have blood pressure measured as part of the study assessment. This blood pressure reading will be collected using a standardized protocol. Participants will be asked to remain seated for 5 minutes prior to the reading. Blood pressure will then be measured three times in a seated position with one minute rest between readings using the Dinamap 9300XL monitor. Healthcare Utilization: This information will be extracted from electronic medical records (EMRs) for the following services: primary care, hospitalizations, and emergency room visits. Total number of visits and number of visits to each service will be calculated for all-cause, mental health, T2D, and hypertension related, separately. Duration of stay will also be assessed.41,42 Based on previous experience of the research team, over 70% of participants will receive their non-bariatric care in the TU or Penn systems during the study. Therefore, we will be able to obtain utilization records through the EMR. However, to ensure complete data capture, we will also use a standardized and validated method employed in the Action for Health in Diabetes (Look AHEAD) study which assesses health services utilization using interviews at study visits.43 Medication Adherence: Among individuals with T2D and hypertension, medication adherence will be calculated, separately, using EMR data for pharmacy fills. We will use the prescription-based proportion of days covered (PDC) method to calculate adherence during the first and second year following surgery. PDC numerator will be defined as number of days with medication available to take between the date of the first medication fill during each time period (Year 1 and 2, separately) to the date of the last fill within the period, and the denominator will be the number of days between the date of the first and last fills during the period.44 Adherence will be defined as a PDC80%. In anticipation of missing EMR data on pharmacy fills, during the baseline, 6-, 12-, and 24-month study visits, we will administer the K-Wood-4 Medication Adherence Scale, a 4-item self-report questionnaire, to assess adherence and provide a way to validate results obtained from the EMR. Temple Health participants will have the option of completing the above assessments in English or Spanish. Participants whose surgery date is scheduled greater than 90 days after their baseline assessment (due to delays in scheduling surgery) may be asked to return to the clinic to complete a portion of the assessment. Participants will be asked to complete the ASA 24 hour dietary food recall and the impulsivity tasks (described above) within approximately 2-8 weeks prior to surgery in order to ensure that these data are within the appropriate time frame prior to surgery. We anticipate that this portion of this assessment will take approximately one hour to complete. If participants are willing to return to the clinic to complete these two portions of the assessment, they will be compensated \$25 for their time.

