
with a 3 level time (6m, 12m, and 24m) x continuous (change), for the different nutrient categories. Missing data The best approach to handling missing data is not to have any, by establishing procedures that correct missingness as it is happening within sessions, and by robust retention efforts as detailed above. In spite of our best efforts, it is likely that some subjects will not provide complete data, by dropping out of the study, by missing an assessment, or by failing to complete all assessments in a session. We will adopt analysis practices that mitigate the impact of missing data. First, all analyses will be conducted using the intention-to-treat (ITT) principle, in which all available data on all participants are included. This approach minimizes bias if individuals drop out for different reasons. In an obesity treatment study, a participant lost to follow-up may be an informative dropout. As long as the missing at random assumption is not violated, attrition related to observed variables (i.e., informative dropout), is a missing or unbalanced data scenario that can be accommodated by the proposed mixed effects models. Furthermore, sensitivity analyses (e.g. baseline carried forward, as treated analysis, various multiple imputation methods, pattern-mixture models) can be conducted and results can be compared to those found with the mixed models. An additional cause of missing data will be item non-response. In the event of items missing at random on survey measures, missing items will be imputed prior to calculating final scores using conditional means, estimated with an iterated version of Bucks method,142 and implemented using the EM algorithm in conjunction with ordinal logistic regression.

The following documents are currently attached to this item:

There are no documents attached for this item.

Are you conducting research outside of the United States? No

Data confidentiality

- **x** Paper-based records will be kept in a secure location and only be accessible to personnel involved in the study.
- x Computer-based files will only be made available to personnel involved in the study through the use of access privileges and passwords.
- x Prior to access to any study-related information, personnel will be required to sign statements agreeing to protect the security and confidentiality of identifiable information.
- x Wherever feasible, identifiers will be removed from study-related information.

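### Dividing T2D and hypertension cases by all participants lets missing follow-up data alone lower apparent prevalence, mainly for T2D

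*Combined protocol and SAP*

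**What the plan says.** The prevalence definitions stand under Study Procedures (Procedures, Prevalence and Control of Chronic Diseases) and are repeated under Administration of Surveys and/or Process.

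- T2D: "Prevalence will be calculated using number of participants with T2D as the numerator and total number of participants as the denominator". Hypertension: "Prevalence will be calculated using number of participants with hypertension as the numerator and total number of participants as the denominator".
- T2D "will be defined as HbA1c 6.5% and glucose 7.0 mmol/L (126 mg/dL), or use of antidiabetes medication". For the other disease, "hypertension will be defined as SBP130 mm Hg, or DBP80 mm Hg, or use of antihypertensive medication". Medication use alone is therefore enough to make a case of either.
- HbA1c and glucose are taken from the electronic medical record: "Participants will not be asked to have additional blood draws as part of the study".
- Blood pressure has two routes. It is extracted from the record, including surgical follow-up, and "Participants will have blood pressure measured as part of the study assessment".
- Control of each disease is calculated only among those who have it. Prevalence carries no such limit, and nothing ties it to people assessed at the visit.

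Secondary outcomes are due at 0, 6, 12 and 24 months. The Missing data part of the Analysis Plan concedes that "it is likely that some subjects will not provide complete data". Its remedies are mixed models and imputation of survey items. Multiple imputation appears only among optional sensitivity analyses set against the mixed models. The Analysis Plan names no model for a binary prevalence outcome.

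**The concern.** The numerator needs evidence: two laboratory values, a blood pressure, or a medication record. The denominator needs only enrolment. Under a literal reading, a person with no evidence is arithmetically a non-case.

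The T2D laboratory criterion adds to this. It requires both HbA1c and glucose, so if one is missing and the other meets its threshold, the laboratory route cannot settle the case. The plan backs up pharmacy-fill data with a questionnaire and utilization data with interviews, but gives no backup for laboratory values.

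What is at stake is the reported course of both diseases after surgery. A shortfall from missing data runs in the same direction as the improvement expected after bariatric surgery, so it would look plausible and could go unnoticed.

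**Working it through.** The documents state no prevalence, dropout rate or expected change for these outcomes, so there is no planned figure to reproduce. The inputs are assumptions:

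- p, true prevalence, unchanged over time: 30%.
- m, share of participants without the laboratory (or blood pressure) components at a visit, unrelated to disease: 15% or 30%.
- c, share of the cases in that group who are still found through medication: 0, 50% or 80%.

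**Step 1, the plan's formula taken literally.** Apparent prevalence = p(1 − m) + p·m·c.

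- m = 30%, c = 0: 0.30 × 0.70 = 21.0%.
- m = 30%, c = 80%: 0.21 + 0.30 × 0.30 × 0.80 = 0.21 + 0.072 = 28.2%.
- m = 15%, c = 0: 0.30 × 0.85 = 25.5%.
- m = 15%, c = 80%: 0.255 + 0.30 × 0.15 × 0.80 = 0.255 + 0.036 = 29.1%.

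The shortfall is p·m·(1 − c), a relative fall of m(1 − c) whatever p is. With c = 0, it runs from 0.25 × 0.10 = 2.5 points to 0.80 × 0.30 = 24 points over p from 25% to 80% and m from 10% to 30%. A false change over time also requires m to differ between visits. If m were the same at baseline and at 24 months, the level would be wrong but the trend would not.

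**Step 2, the obvious repair.** Suppose the denominator became everyone whose status can be determined, with medication use known for all. A medicated participant without laboratory values is then determinable and an unmedicated one is not. Prevalence = [p(1 − m) + p·m·c] / [(1 − m) + p·m·c].

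| m | c | Literal formula | Anyone determinable | Complete components |
|---|---|---|---|---|
| 30% | 0 | 21.0% | 30.0% | 30.0% |
| 30% | 50% | 25.5% | 0.255/0.745 = 34.2% | 30.0% |
| 30% | 80% | 28.2% | 0.282/0.772 = 36.5% | 30.0% |

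At c = 80% this repair is 6.5 points too high, against 1.8 points too low for the literal formula.

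**Step 3, complete components.** If numerator and denominator are both limited to people with all components, prevalence = p(1 − m)/(1 − m) = 0.21/0.70 = 30%. This is correct when missingness is unrelated to disease.

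**Step 4, bounds at m = 30%.** With c = 0, the range is 21.0% (no missing participant a case) to 21.0% + 30.0% = 51.0% (all of them cases). With c = 80%, the unresolved share is 0.30 − 0.072 = 22.8%, so the range is 28.2% to 51.0%.

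**The case against.** The strongest reply is that the plan nowhere says unknown status means no disease. The phrase about all participants comes just before control, which is limited to those with the disease. It may only mark that contrast and not set a rule for missing data. The Missing data text promises to use all available data, which is compatible with counting only people assessed at the visit. This stands as a point about intent. It does not remove the problem: the written formula has no such limit, the two readings give different results, and no other text chooses between them.

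Three further points stand and limit the finding:

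- Not everyone with a missing laboratory value or visit becomes a non-case. Medication alone makes a case, and blood pressure may be in the record when a study visit is missed. Missing laboratory values have no bearing on hypertension.
- A reader might infer that attrition would be reported as remission. Remission is not an outcome here; the plan defines prevalence and control.
- A reader might infer a false decline from a nearly complete baseline, or a biased comparison of predictor groups. Accrual runs until 300 adults have completed baseline visits, so loss to study visits comes mostly later, but no completeness figure for laboratory values is given at any time point. The Abstract says the predictors will be related to these outcomes, but the Analysis Plan specifies no group test for them.

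**Conclusion.** The concern holds as a defect in the stated formula, not as a demonstrated false fall in prevalence. Followed literally, the formula understates prevalence at any visit where some participants cannot be classified, and nothing in the Analysis Plan firmly repairs this.

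T2D is the main outcome affected; hypertension is less exposed. At an assumed 30% prevalence and 30% missing, the understatement is 9 points if medication finds none of the missing cases and 1.8 points if it finds 80% of them. These sizes rest on assumed prevalence, missingness and medication capture, and on missingness unrelated to disease. The study is powered on weight change under Specific Aim 1, which is untouched.

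**What to change.** At each visit, restrict both numerator and denominator to participants with all components needed for classification. For T2D these are HbA1c, glucose and medication information; for hypertension, blood pressure and medication information. Do not use anyone whose status happens to be determinable: that keeps medicated cases, drops unmedicated non-cases, and biases prevalence upward.

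State how a participant with only one of HbA1c and glucose is handled, and report the number unclassifiable at every visit.

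For the analysis, specify either multiple imputation of the missing components or a repeated-measures logistic model on the complete-component data, with best-case and worst-case bounds. Imputation has the advantage of using the medication information of people without laboratory values. The complete-component proportion alone is sound only if missingness is unrelated to disease.

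No new data collection is needed. The cost is a change of wording, somewhat wider intervals at later visits, and a little more analysis work.

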
Primary outcome variable(s)

All primary outcomes will be measured at 0, 6, 12, and 24 months postoperatively. Specific Aim 1: weight change

Secondary outcome variable(s)

All secondary outcomes will be measured at 0, 6, 12, and 24 months postoperatively. Secondary aims call for examining relationships between primary outcomes and some additional variables. These additional variables include psychosocial status, dietary intake, physical activity, prevalence and control of T2D and hypertension, health services utilization, and adherence to antidiabetes and antihypertensive medication.

Background

Bariatric surgery is an increasingly utilized treatment for the growing number of individuals with a body mass index (BMI) of 40 kg/m2 or 35 kg/m2 in the presence of obesity-related comorbidities. Early results are promising, with patients losing 20-35% of their initial body weight in the first 6-18 months after surgery and experiencing improvements in obesity-related comorbidities. These outcomes,

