Bariatric surgery poses several significant risks, including: gastric perforation, staple line disruption, disruption of the gastrojejunal anastomosis with a leak, deep vein thrombosis, pulmonary emboli, and death. These risks will be addressed with patients as part of their informed consent for surgery. Participation in the proposed study has no impact on the risks associated with surgery. WE NOTE THAT BARIATRIC SURGERY IS BEING PERFORMED INDEPENDENTLY OF THIS RESEARCH (I.E., SURGERY IS NOT A STUDY PROCEDURE). Patients overall physical health will be monitored by their bariatric surgeon and/or primary care physician. Thus, these professionals will be primarily responsible for monitoring patients health as they lose weight after surgery, including dietary intake and malnutrition, hypotension or hypoglycemia, or risks associated with increased physical activity. If these or other medical issues come to the attention of research study staff during a study visit, the patient will be encouraged to communicate these findings to his or her physician. The psychometric and more objective neurocognitive tests present little risk to participants. Similarly, the structured clinical interviews are believed to present little risk to participants. Finally, there is the potential that individuals connected with the study will see personal health information not relevant to the study. Risks of complications will be reduced by regularly monitoring participants progress. Safety reports will be created by the Research Coordinators and sent to the PIs and Data Safety and Monitoring Board (DSMB). Study staff will make clear that subjects are not obligated to participate in the study and that their answers will be held strictly confidential. Questionnaires will not contain any identifying information, thus, ensuring the confidentiality of subjects responses. Code numbers will be assigned to each subject to maximize anonymity when entering and analyzing data. All data collected will be received and kept in a locked filing cabinet and on a password-protected computer by the Research Coordinators. Subjects will be informed that they can withdraw from the study whenever they wish and that their withdrawal will not affect the medical care they receive.

Potential Study Benefits

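### The PDC adherence rule has no provision for prescriber-ordered interruptions, so a long ordered stop-and-restart within one year labels a compliant patient non-adherent

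*Combined protocol and SAP*

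**What the plan says.** The definition is in the combined protocol and SAP, Study Procedures, under Medication Adherence.

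- **Source.** For participants with type 2 diabetes or hypertension, "medication adherence will be calculated, separately, using EMR data for pharmacy fills".
- **Periods.** The method is used "to calculate adherence during the first and second year following surgery", each year on its own.
- **Numerator.** "PDC numerator will be defined as number of days with medication available to take", counted from the first to the last fill of the period.
- **Denominator.** "the denominator will be the number of days between the date of the first and last fills during the period".
- **Cut-off.** "Adherence will be defined as a PDC80"%. The comparison sign was lost when the text was read; I take it as at least 80%.
- **Back-up.** A four-item self-report scale is given at baseline and at 6, 12 and 24 months because fill data may be missing, and "to assess adherence and provide a way to validate results obtained from the EMR". Nothing says what happens when the scale and PDC disagree.

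The section on secondary outcome variables lists "health services utilization, and adherence to antidiabetes and antihypertensive medication". The Analysis Plan does not mention adherence, so nothing there modifies the rule.

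**The concern.** PDC is meant to show whether patients kept themselves supplied with a drug they had been told to take. As written, each uncovered day between the first and last fill counts against the patient, whether a refill was missed or the prescriber had told the patient to stop. The two cannot be told apart because no stop, hold or dose-change date enters the formula.

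Ordered changes are plausible in this population. The Background section expects comorbidities to improve with weight loss, which typically peaks about 12 months after surgery. The section on potential study risks gives the treating physicians responsibility for "monitoring patients health as they lose weight after surgery, including dietary intake and malnutrition, hypotension or hypoglycemia". Year 1 PDC covers that period.

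At stake is the meaning of a named secondary outcome. Some participants labelled non-adherent could be people who did what they were told. The self-report scale could then disagree with PDC for a reason unrelated to adherence.

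**Working it through.** The plan gives no expected adherence rate, sample size or power for this outcome, so there is no figure to reproduce. I applied the written rule to hypothetical patients who follow every order exactly.

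**Inputs from the document:** the numerator, denominator, yearly periods and 80% cut-off above. **Assumptions, not in the document:** one drug per condition; 30-day or 90-day fills; each ordered stop falls as the supply in hand runs out; pauses of 14 to 180 days; dose cuts of one half.

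**Threshold.** Let D be the days from first to last fill and G the uncovered days inside that interval, all other days being covered. Then PDC = (D − G)/D, which is below 0.80 only if G > 0.20 × D.

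- D = 360: 0.20 × 360 = 72, so 73 days or more
- D = 180: 0.20 × 180 = 36, so 37 days or more
- D = 90: 0.20 × 90 = 18, so 19 days or more

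**Ordered stop and restart, 30-day fills, about a one-year window:**

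| Ordered pause (days) | Covered / interval | PDC | Label |
|---|---|---|---|
| 14 | 330/344 | 95.9% | adherent |
| 30 | 330/360 | 91.7% | adherent |
| 60 | 300/360 | 83.3% | adherent |
| 73 | 270/343 | 78.7% | non-adherent |
| 90 | 270/360 | 75.0% | non-adherent |
| 120 | 240/360 | 66.7% | non-adherent |
| 180 | 180/360 | 50.0% | non-adherent |

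A shorter window is less forgiving. Take fills on days 0 and 30, an ordered stop at day 60, and fills on days 240, 270, 300 and 330. Covered days up to the last fill are 5 × 30 = 150, so PDC = 150/330 = 45.5%. With the 180 ordered-off days removed from the denominator, PDC = 150/(330 − 180) = 150/150 = 100%. The same correction gives 100% in every row of the table.

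**Ordered permanent stop.** Fills on days 0, 30 and 60, then none: 60/60 = 100%. The interval closes at the last fill, so there is no penalty.

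**Ordered dose reduction.** A 90-day fill on day 0 is halved in dose on day 30. The remaining 60 days' supply lasts 120 days, and the next and last fill is on day 150.

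- Supply left at the old dose: 90/150 = 60%.
- Supply counted at the new dose: 150/150 = 100%.

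With 30-day bottles stretched to 60 days and supply left at the old dose, one bottle gives 330/360 = 91.7%, two give 300/360 = 83.3% and three give 270/360 = 75.0%. A new prescription carrying the correct days' supply leaves no gap.

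**The case against.** A reader might infer that any ordered dose cut or pause turns a compliant patient into a non-adherent one. The text does not support that. Pauses of 14, 30 and 60 days stay above 80% in a window of about a year, and a permanent stop costs nothing. In the dose-cut case the patient has usable drug on all 150 days, and the numerator's wording can fairly be read to count them. The 60% result needs days' supply to be frozen at the old dose, which the plan does not say.

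A reader might also infer a known bias: those who lose most weight have drugs paused most often, so associations with psychopathology and impulsivity shrink or reverse. That cannot be shown. Only patients who restart within the year are penalised, and the Background section links weight regain to loss of health benefits, so restarters could be the poorer responders. The bias would then run the other way. The aims predict no direction for adherence, and no adherence analysis is specified.

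It is also fair to say that the method is called prescription-based and cites a source, and that the self-report scale might expose some discrepancies. Neither removes the problem. The formula as written uses fill dates and no order dates, and the scale has no stated power to correct PDC.

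What stands of the objection narrows the point. The long stop-and-restart remains: there the written rule gives the wrong label.

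**Conclusion.** The concern holds in a limited form. The rule makes no provision for prescriber-ordered interruptions. It mislabels a compliant patient when the drug is stopped and restarted within the same year and the uncovered gap exceeds 20% of the first-to-last-fill interval. Shorter ordered pauses understate PDC but leave the label unchanged. For dose reductions the fault is an ambiguity, which becomes an error only if supply is kept at the old dose.

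The percentages rest on the assumed fill patterns. Supply left over at the stop, or coverage counted across several drugs for one condition, could shorten the uncovered gap; the plan does not say whether coverage is counted per drug or per condition. The documents give no frequency of ordered changes, so neither the number misclassified nor the direction of bias can be derived. Only a secondary outcome is touched; the primary weight analysis is unaffected. The rule should be settled before PDC is computed.

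**What to change.** Under Medication Adherence in Study Procedures:

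- Exclude from both numerator and denominator the days between a documented prescriber stop or hold order and the restart order in the medical record. Do not exclude days on which an order merely lapsed, since a patient who fails to seek renewal would then be scored as adherent.
- Count days' supply at the prescribed dose in force from the date of each documented change.
- Report PDC with and without this adjustment for all participants, so that one definition applies to everyone within each analysis.

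Moving the end of the interval would not do the same job, because these gaps lie inside it.

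The cost is some programming and the extraction of order dates from the same records that supply the fills. The record review described for the study lists psychiatric medications but not antidiabetes or antihypertensive orders, so this is an added item. Order dates may be incomplete for participants treated elsewhere: the plan expects just over 70% to receive their non-bariatric care within the two health systems. For the rest, the adjusted figure may differ little from the unadjusted one, and the report should say so.
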